
PURPOSE

We propose to conduct the first randomized controlled trial to test whether a cessation intervention in the PED setting can reduce caregiver smoking and decrease children's SHSe.

Primary Aim 1: To evaluate the efficacy of the SBIRT compared to Healthy Habits Control (HHC) condition. Primary outcomes are self-reported prolonged abstinence and point prevalence at 6-weeks and 6-months post-enrollment, validated in all participants via expired carbon monoxide and salivary cotinine. Secondary outcomes include number of cigarettes smoked, quit attempts, readiness to quit, and use of cessation resources.

Hypothesis 1: Caregivers who receive the SBIRT will have higher prolonged abstinence and point prevalence cessation rates compared to caregivers in the HHC condition.

Primary Aim 2: To evaluate the efficacy of the SBIRT on reducing children's SHSe. Outcomes are caregiver reports of total home/car smoking bans and reductions in SHSe (validated using salivary cotinine in children).

Hypothesis 2: Children of SBIRT caregivers will have higher total home/car smoking bans and lower home/car smoking exposure compared to children of HHC caregivers.

Primary Aim 3: To explore mediators and moderators of the SBIRT outcomes.

Hypothesis 3: The SBIRT intervention effect on prolonged abstinence and point prevalence cessation rates will be mediated by the caregiver's perception of the risk of smoking on their child's health and the caregiver's motivation to quit over time. The intervention effect will be moderated and attenuated by factors such as household smokers, financial strain, and low social support to quit.

Secondary Aim 1: To conduct a cost analysis to determine the numbers of SHSe-related PED visits and hospitalizations in children of caregivers in the SBIRT condition compared to children of caregivers in the HHC condition. This will provide a basis for a future, full-scale cost-benefit analysis.

Secondary Aim 2: Using the findings from this project and our prior research, we will develop a manual of operations and a comprehensive package of provider and patient materials that will be disseminated for use in other PEDs and EDs nationwide.

Secondary Aim 3: To quantify the prevalence and identify correlates of Cannabis Smoke Exposure and SHSe among SHS-exposed PED patients.

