The prevalence, risk factors, and clinical effects of child cannabis smoke exposure (CSE) compared to SHSe is also important to understand. However, little is also known on the prevalence of CSE and SHSe among PED patients and related risk factors, health effects, and healthcare utilization. There is currently no precise estimate of CSE among SHS-exposed children. Therefore, this study will also quantify the prevalence and identify correlates of CSE and SHSe among SHS-exposed PED patients.

METHODS

Study Design Overview

Design. We will use a randomized, two-group design for the proposed study. We will recruit 750 caregivers who smoke and present to the PED with their child for a SHSe-related chief complaint. Participants will be randomly assigned to one of two study conditions: (1) Screening, Brief Intervention, and Assisted Referral to Treatment (SBIRT) Condition or (2) Healthy Habits Control (HHC) Condition.

Pool of Potential Participants: Approximately 6,000 pediatric patients with a SHSe related illness will present to the PED with their caregiver in a 30 month period. Based on our research, we know that approximately 85% of caregivers (N=5,100) will be able to be screened by a Clinical Research Coordinator (CRC); at least 35% will be smokers (N=1,785); and at least 80% of these caregivers will consent (N=1,428).

Assessments. Caregivers will complete an informed consent. They will also complete the baseline electronic assessment on a study tablet. Caregivers will be assessed with questionnaires at baseline, approximately 6-weeks, and approximately 6-months post-enrollment. We will also contact participants via text messaging, email, phone, or social media to remind them of study participation. Should we discover any missing data, we may call participants or conduct home visits at any time point during the study. Before conducting these additional home visits, we would contact the participant first to obtain permission to conduct the home visit. We will assess all children at baseline and at approximately 6-weeks post-enrollment. At 6-weeks we will contact participants via phone calls, emails, social media, text messaging,,and home visits to children and caregivers in the SBIRT and HHC condition to: 1) verify abstinence on 100% of caregivers who report that they have not smoked in the past

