7 days via expired carbon monoxide testing and/or salivary cotinine, 2) obtain a follow-up salivary cotinine level on 100% of children to validate total smoking bans, and 3) complete assessment of outcomes. At 6 months, we will assess all caregivers via phone or email. We may contact them via social media or text messaging as well. Participant's privacy will be maintained when contacting them through social media by sending messages that only the participant can see via social media. PHI will not be used on these messages. Should the caregiver report abstinence and smoking bans, a home visit will be conducted to validate self-reported abstinence and total home smoking bans via salivary cotinine on the child and via expired carbon monoxide testing and/or salivary cotinine on the caregivers during home visits. Follow-ups may be conducted at CCHMC hospital if the participant already has a scheduled appointment at the hospital. If study staff is unable to make contact with the family during the course of the study to schedule the follow-ups an unannounced home visit may be conducted in order to complete study procedures.

Randomization. We will stratify by gender of the primary caregiver and stage of readiness to quit smoking where participants will be in stages 1: pre-contemplation, 2: contemplation 1 or 2, or 3: preparation;^{41,42} thus there will be 8 strata for randomization. A random block randomization scheme will be compiled by the study biostatistician prior to the start of the study, and used by the CRC to allocate participants to each condition. The biostatistician has a SAS® program for creating the randomization scheme that has been tested and used for other studies. As it is anticipated that there will be fewer male caregivers, the random blocks used will be smaller than for the females. The randomization scheme will be accessed by the CRC by logging into a dedicated website and entering the gender and readiness to quit stage, the study group assignment and a study identification number will be returned. Backup will be opaque envelopes, kept within the PED with stratification and study identification number marked on the outside.

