1) NRT: All caregivers who do not have any contraindications to NRT will be offered a free, 6 week supply of their choice of NRT patches or lozenges. NRT will be stored in a locked cabinet in the CRC office in the PED. The clinical counselors/intake coordinators/research coordinator will screen all participants for eligibility and for any contraindications to NRT using a screening checklist (See Appendix F). If there are any questions about eligibility for NRT, the clinical counselors/intake coordinators/research coordinators will contact the PI or other study MD. The PI or other study MD will be available in-person or by phone to address any questions. This arrangement has worked well for our most recent cessation trial (5K22CA163747). The screening checklist will be sent electronically to the PI or other study MD if there are any contraindications to NRT, who will approve/disapprove the distribution of NRT to the caregiver. If there are no contraindications to NRT on the checklist, the form will not be sent to the PI or other study MD, and the research coordinator may dispense NRT to the caregiver. Study staff will instruct the caregiver on NRT use and they may use expired NRT to demonstrate to caregivers how to place the patch on and to show them what the lozenge looks like. In addition, all caregivers will be provided a home visit for follow-up at 6-weeks during which they will be asked if they were given NRT at baseline, and if so, if they used the NRT. If they used approximately 80% of the NRT and wish to receive more NRT, they will be screened for eligibility and for any contraindications to NRT using the screening checklist in the same manner listed above as at baseline (See Appendix I). If eligible, they will receive 6 weeks of NRT. If a home visit is not possible, the survey will be completed via phone or email and the sample may be obtained from the family via mail. An approximately four week window for follow-up will be used. The follow-up may also be completed at CCHMC or another mutually agreed upon location, if the participant has an already scheduled appointment.

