2) Immediate connection to cessation resources: All caregivers will be provided an "Assisted Referral" based on preference. These options will include: a) Quit Line: The clinical counselors/intake coordinators/research coordinators will dial a direct number to the Ohio QL. A QL counselor will initiate brief counseling which may include counseling calls and free NRT⁵³ If the caregiver prefers, a fax referral may be completed and faxed to the QL.

b) Web-based: the clinical counselors/intake coordinators/research coordinators will help the caregiver log onto smokefree.gov using the computer that is in every patient's PED room. This site has a variety of interactive tools including a LiveHelp online "chat" service, SHSe and cessation quizzes, a cessation mobile app, and other helpful resources; c) Text Messaging: the clinical counselors/intake coordinators/research coordinators will help the caregiver sign up with smokefreeTXT. These free mobile services provide encouragement, advice, and tips to help smokers quit.

3) Intervention Materials: To supplement the baseline intervention, we will provide free caregiver materials shown to be effective in previous studies^{54,55} (See appendix B). All or some of the materials listed in Appendix B will be provided to the caregiver, as applicable. Booster messages with reminders of the benefits of quitting will be sent by email, mail, or text message for 12 weeks.

Feasibility and Generalizability: The SBIRT is feasible for deployment in PEDs and general EDs that serve both children and adults. The vast majority of these settings have clinical counselors/intake coordinators/research coordinators or equivalent professionals who could be trained to deliver the intervention. SBIRT is streamlined and efficient and can be integrated into acute care. Even in the most time-efficient ED settings, waiting times are inevitable. These provide opportunities for delivery of the SBIRT. The format of the intervention mirrors other successful prevention approaches in the ED setting. Our association with PECARN provides an infrastructure for rapid deployment of the intervention dissemination materials leading to widespread adoption.

The Healthy Habits Control Condition

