We will use GLMM to evaluate the relative effectiveness of the SBIRT versus HHC group on our primary outcomes: point prevalence and prolonged abstinence at 6-months. The analysis will be repeated with caregiver level differences between groups included as covariates. We will use mixed model analysis of covariance, with repeated measures to assess change (controlling for baseline differences between groups) to assess the effect of the SBIRT on secondary outcomes including reduction in use, number of quit attempts, and changes in readiness to quit. Kappa statistic will be used to assess agreement between the caregiver's self-report and the assessment of tobacco use based on expired carbon monoxide levels and/or salivary cotinine at 6 months. It is possible that use of and adherence to the NRT will influence outcomes in the intervention group. In addition, some of the participants in the control condition may obtain NRT during the study interval. We will examine NRT use or dose, defined as self-reported adherence, as a covariate in order to control for this possible relationship.

Analyses for Primary Aims 1-3.

Primary Aim 1, Hypothesis 1: We hypothesize that SBIRT participants will have higher prolonged abstinence and point prevalence cessation rates compared to those in the HHC group. As stated above, our primary approach to the analysis is using multiple imputation, with clinical counselors/intake coordinators/research coordinators included in the model. We shall then use analysis of covariance, to control for any baseline differences of caregivers between conditions. In addition we will also control for motivation to quit, considered a priori as a potential covariate, using the score on the contemplation ladder. As we are stratifying on motivation to quit and caregiver gender, we will initially enter this into the model as an interaction. To address child cotinine as the 6-month outcome, we will use a t-test and then an analysis of covariance to incorporate the variables different at baseline. Incorporating the 6-week outcome values, we will use GLMM invoking GEE for the repeated

measures and also a model including covariates. This approach will be used to assess the intervention's effect on abstinence and point prevalence and child cotinine.

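### Child cotinine is compared between arms at 6 months, but where the collection rule is explicit, 6-month child saliva is taken only after the caregiver reports quitting, or quitting plus smoking bans

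*Combined protocol and SAP*

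**What the plan says.** **Analysis.** Under Analyses for Primary Aims 1-3, Primary Aim 1, the plan states: "To address child cotinine as the 6-month outcome, we will use a t-test and then an analysis of covariance". It then adds mixed models with GEE that bring in the 6-week values. Primary Aim 2 in the same section uses child salivary cotinine as one of two measures of smoke exposure. It looks first at change from baseline to 6 weeks, then at change from 6 weeks to 6 months as a maintenance effect.

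**Collection from all children.** Study Design Overview (Assessments) says: "We will assess all children at baseline and at approximately 6-weeks post-enrollment". It also plans follow-up cotinine for every child at 6 weeks. The HHC Protocol repeats this, and Data Collection and Participant Retention plans home visits to all families at that time.

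**Collection at 6 months.** Caregivers are contacted remotely. The Assessments paragraph then says: "Should the caregiver report abstinence and smoking bans, a home visit will be conducted to validate self-reported abstinence", with child saliva taken at that visit, and the HHC Protocol has the same rule. Follow-up Assessments uses a different trigger: a reported quit. Biochemical Validation mentions 6-month child saliva only as a possibility, and Compensation pays for the 6-month visit only where one applies.

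**Role of cotinine.** Purpose, Primary Aim 2, gives it a validating role: "validated using salivary cotinine in children". Outcome Measures does not list it among the child outcomes, and no power statement covers it.

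**The concern.** A between-arm test has a causal reading because randomisation made the arms comparable. If a child has a 6-month value only when the caregiver reports having quit, the test compares SBIRT quitters' children with HHC quitters' children. Quitting comes after randomisation and is what SBIRT is designed to change, so the two sampled groups need not be alike. An effect on the child that works through quitting is largely conditioned away, because everyone sampled has quit.

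At stake is the biomarker evidence for Primary Aim 2. A real benefit could be missed, or a null or adverse 6-month result could be read as failure of the intervention.

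**Working it through.** **1. The plan's own figure.** Sample Size gives 750 enrolled and 20% attrition: 750 x 0.80 = 600, or 300 per arm. This reproduces.

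**2. Children with a 6-month value under the explicit rules.** Sample Size expects 6-month point prevalence of 12% (SBIRT) and 6.3% (HHC).
- Quit trigger: 300 x 0.12 = 36 and 300 x 0.063 = 18.9, total 54.9 of 600 (9%).
- Quit plus bans: at most the same 55. If half of quitters report bans (assumed), 54.9 x 0.5 = about 27.

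**3. Precision.** The documents give no SD for cotinine and no alpha. I assume a log-scale SD of 1.0 to 1.5 and a two-sided 5% test. The ratio detectable with 80% power is exp(-2.80 x SD x sqrt(1/n1 + 1/n2)).
- 36 vs 19: sqrt(1/36 + 1/19) = 0.284, giving 0.45 (SD 1.0) and 0.30 (SD 1.5).
- 300 vs 300: sqrt(2/300) = 0.082, giving 0.80 and 0.71.

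For a true 20% reduction in every child (assumed), with no correlation between cotinine and difficulty of quitting, simulated power is about 12% (SD 1.0) or 7% (SD 1.5) in the triggered set. With all 300 per arm it is 78% or 45%.

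**4. Direction and size of bias (illustrative).** Suppose a latent normal difficulty of quitting, with the easiest fraction p of each arm sampled. The mean difficulty of those sampled is -phi(z_p)/p.
- SBIRT, p = 0.12: -1.667. HHC, p = 0.063: -1.964. Difference 0.297.
- The shift in log cotinine is 0.297 x rho x SD. At rho = 0.6 and SD = 1.5 (both assumed) it is 0.268, a ratio of exp(0.268) = 1.31 with no true effect. At rho = 0 the ratio is 1.00.
- At rho = 0.6, the 5% t-test falsely favours HHC in about 11% of simulated trials and SBIRT in about 0.4%.
- If both arms trigger equally, the difference is zero and the error is nominal (about 2.5% each way).

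**5. Alternatives.** With baseline adjustment, the detectable ratio is exp(-2.80 x SD x sqrt(2/n) x sqrt(1 - r^2)), with baseline correlation r of 0.5 to 0.7 (assumed).
- Six weeks, 200 to 300 sampled per arm (assumed, allowing for missed visits): 0.69 to 0.85.
- Six months, a random 100 per arm: 0.60 to 0.75.

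**The case against.** **The documents leave room for wider sampling.** Staff may visit to fill missing data, and "an unannounced home visit may be conducted in order to complete study procedures". Follow-up may take place at the hospital. The retention section lists a 6-month visit payment without a condition, child cheek swabs are planned at 6 months, and Confidentiality/Security mentions in-person surveys. Purpose, Primary Aim 1, says outcomes are "validated in all participants via expired carbon monoxide and salivary cotinine", though this concerns caregivers. These lines stand as evidence of ambiguity. None schedules 6-month saliva for children whose caregivers report neither a quit nor a ban. A reader might infer that selective sampling is settled; the text supports only that it is what the explicit rules say.

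**A ban-only trigger would yield far more children.** A reader might count them from the plan's ban rates, but no section states such a trigger. The calculation would also treat the 12-point difference in the Power section as expected, when it is only the detectable difference. Figures on that basis are illustrative and depend on the assumed difference between arms.

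**The later models may help.** The ANCOVA and GEE can use baseline and 6-week cotinine, and 6-month caregiver report is sought from everyone, so the reason for missingness is largely observed. This could reduce the bias, which I quantified only for the t-test. But under the explicit rules no untriggered child has a 6-month value, so these models extrapolate untestably. The imputation and weighting in Preliminary Analyses are written for loss to follow-up and would face the same limit.

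**The bias model is invented.** True: step 4 shows direction and plausible size only. The small sample and the selection on reported quitting do not depend on it.

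**Conclusion.** The analysis and the collection plan do not match, and this should be fixed. Followed as explicitly written, the 6-month comparison rests on about 36 vs 19 children, at most 55 of 600, and does not compare the randomised groups. These counts use the plan's own quit and retention rates; the detectable ratio of 0.30 to 0.45 rests on the assumed SD.

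If the arms differ in quitting and cotinine is higher where quitting is harder, the bias runs against SBIRT, illustratively up to a ratio of about 1.3. A negative correlation would reverse it. If the arms trigger equally, the error rate is nominal, but the result still describes only the triggered subgroup.

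Three stronger conclusions are tempting but unsupported. The flaw does not threaten the caregiver abstinence outcomes, which do not use child saliva. It is unlikely to create a false claim of efficacy under the stated assumption. It does not undermine the whole maintenance contrast in Primary Aim 2, which also covers bans and caregiver-reported exposure, both assessed without child saliva. The 6-week cotinine comparison is free of this selection, apart from ordinary attrition and missed visits.

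**What to change.** 1. Reconcile Purpose, Study Design Overview (Assessments), HHC Protocol, Follow-up Assessments and Biochemical Validation on which children give saliva at 6 months.

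2. If all children, or a random subsample chosen independently of caregiver report, are sampled, keep the 6-month between-arm test for that set. At the $35 visit payment in Compensation:
- Random 100 per arm: 200 x (1 - 55/600) = 182 extra visits ($6,370), rising to 200 x (1 - 27/600) = 191 ($6,685) if only 27 are triggered.
- All 600: 545 extra ($19,075) to 573 ($20,055).

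   Staff and assay costs are extra. For the 6-week visit the plan already allows that "the sample may be obtained from the family via mail"; extending this to 6 months could replace some visits.

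3. Otherwise, make the baseline-adjusted ANCOVA of log child cotinine at 6 weeks the between-arm cotinine analysis, in line with the first step of Primary Aim 2. Remove 6-month cotinine from the between-arm t-test, ANCOVA and GEE models, and from the cotinine part of the maintenance contrast. Keep that contrast for bans and reported exposure. Report 6-month cotinine descriptively, as validation of reported quits and bans. State how undetectable values, recorded as 0, are handled before taking logs.

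Option 3 needs no new samples but has a real cost. The SBIRT section says: "Booster messages with reminders of the benefits of quitting will be sent by email, mail, or text message for 12 weeks". Six weeks falls inside that period, so no post-intervention between-arm cotinine claim could be made.

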2. Financial Strain. Three items will be used to measure financial strain.⁷⁴ The questions are: "How difficult is it for you to live on your total household income right now?", "In the next three months, how often do you think that you or your family will experience a bad time such as poor housing or not having enough food?", and "In the next three months, how often do you expect that you will have to do without the basic things that your family needs?" The three items will be measured on five-point scales and averaged to create a financial strain score ($\alpha = .802$). Higher scores will reflect more financial strain.

3. Risk perception to child. Perceived vulnerability regarding the effects of his/her smoking on their child will be assessed using adapted measures by Borelli et al. Perceived Vulnerability-Child will be measured with items including: "How concerned are you that smoking will make your child's illness worse?". Higher scores indicate higher perceived vulnerability.⁷⁷⁻⁷⁹

6. Benefits of quitting. We will assess whether the caregiver perceives that quitting smoking would have a beneficial effect on their child using the adapted precaution-effectiveness measures by Borelli, et. al. Precaution Effectiveness-Child (PE-C) will be measured by items including: "If you stop smoking, how much would that decrease your child's symptoms?". Higher scores indicate higher perceived vulnerability.⁷⁷⁻⁷⁹

7. Child's SHSe. Child's SHSe will be assessed by asking about family and other individuals with whom the child came in contact during the past week who smoke, locations of smoking, and number of cigarettes smoked. We will use questions adapted from previous studies.^{52,80-83} Caregivers who report no smoking indoors, outdoors, or in a car will be considered to have a complete smoking ban. Epic chart review will be conducted to assess SHSe-related PED visits and hospitalizations to CCHMC for 6-months prior to baseline.

8. Healthy Lifestyle Habits. We will assess healthy lifestyle practices (daily fruit/vegetable/sugary drink consumption, daily exercise and screen time) of all children.

9. Consumer satisfaction measure. SBIRT and HHC caregivers will complete a satisfaction survey measuring intervention satisfaction and perceived usefulness.⁸⁴

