Sample Size. Our estimate of the number of caregivers that we plan to enroll is based on the average number of unique patients and the smoking prevalence of caregivers seen in a 12-month period in the PED at CCHMC. Based on enrollment in previous studies (which had average annual enrollment of 300-350 caregivers), and a 30 month chart review on the number of annual visits for patients with SHS-related complaints (at least 6,000), we are conservatively expecting to enroll 300 caregivers who smoke over 12 months, for a total of 750 caregivers in 30 months. To obtain the effective sample size for power analyses of outcomes, the sample size must be adjusted for potential attrition of approximately 20% at 6 months, although all efforts will be used to decrease this attrition rate, leaving a total of 600; 300 per group.

Estimate of effect sizes: Evaluation of outcomes. Based on the recommendations of Hughes et al.,^{85,86} we will use 2 criteria for abstinence: 6-month point prevalence and prolonged abstinence at 6-months. Based on a similar prior study, we expect that 6-month point prevalence in the HHC condition will be 6.3%.⁵⁴ For prolonged abstinence, we are basing our estimation on the 2.1% rate for the HHC and 7% rate for SBIRT. We are conservatively estimating a point prevalence cessation rate of 6.3% and prolonged abstinence rate of 2.1% in the HHC group.⁵⁴ We are basing our estimate of 6-month point prevalence of the SBIRT group on the odds ratio derived from meta-analyses assessing the effectiveness of NRT vs. a control, ranging from 1.4-4.6,⁵⁴ to give a cessation rate of 10-12% in the SBIRT group. However, since a clinical counselor/intake coordinator/research coordinator will be conducting the intervention, we expect high compliance in implementation. Thus, we are estimating a cessation rate of 12% in the SBIRT group. Similarly, for prolonged abstinence, we are assuming a rate of 7% in the SBIRT group.

Power (Table 2). Power analyses are based on estimates of differences in both 6-month point prevalence and 6-month prolonged abstinence between groups. With 300 subjects in each group, we would have 80% power to detect an increase of 6.4% in cessation rate. However, assuming a multiple imputation approach, we would be able to detect a 5.5% increase in cessation rate.

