For 6-month abstinence, we can detect an increase of 4.5% with 300 subjects per group and 4.2% with the multiple imputation assumption. These estimates are consistent with the predicted cessation rates shown above and published rates.^{54,93} For analyses based on regression techniques, using hierarchical linear modeling, sample sizes will be more than sufficient. The effect sizes of interest for these analyses are the correlation

Table 2: Estimated Power for varying sample size

N / group	Odds ratio 80% power- prevalence	Odds ratio 80% power- abstinence	Assumption
300	2.16	3.29	20% loss
375	2.00	3.05	Multiple Imputation

coefficients and squared, semi-partial correlations (squared=incremental R^2). To predict caregiver level variables (Primary Aim 1), with a sample size of 750 and 20% lost to follow-up, we will have >80% power to detect a correlation of 0.11 ($r^2=0.013$). For examination of smoking bans (Primary Aim 2), these samples sizes would allow us to detect a difference of 12% with 80% power with 300 per group assuming a rate of between 50% and 65% in the HHC group. Using multiple imputation and 375 per group, we could detect a difference of 11% with 80% power.

Analytic Plan

Data analyses will be conducted at CCHMC and at the University of Cincinnati. A DTA will be established with study investigators at the University of Cincinnati. Data will include demographics, smoking behavior, data from the parent assessments, clinical data, and EMR data. The data will be a limited data set stripped of identifiers. It will be shared on an encrypted file.

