Primary Aim 2, Hypothesis 2: We will evaluate the effectiveness of the SBIRT on total home/car smoking bans and on child SHSe which will be measured by both caregiver report and child salivary cotinine, as recommended by Halterman et al.⁸⁷ The reliability of caregiver's reports will be examined by comparing amount of smoking and SHSe levels reported at 6-months using Pearson's correlations. For validation, we will compare the child's salivary cotinine concentrations for those reporting total home/car smoking bans and those not, we shall also examine the change in cotinine levels from baseline for those initiating bans versus not. The computational procedure will use data from the 2 measurement points, controlling for the within-subject correlation of measures repeated over time.^{97,98} The main analysis will use GLMM, first to assess the intervention effect alone and then including covariates. First, we will investigate immediate intervention effects based on change from baseline to 6-weeks post-intervention. Next, we will investigate change from 6-weeks to 6-months to examine maintenance effects. To examine overall change, we will use GEE, examining linear and quadratic terms for time, group, and group \times time interactions as explanatory variables.⁵² Use of NRT, described above, may be of particular interest as a covariate for this analysis.

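### Aim 2 reads the smoking-ban effect from change since baseline and never fixes the baseline ban as a covariate; conditioning on it is never less efficient and costs nothing

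*Combined protocol and SAP*

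**What the plan says.** Under Primary Aim 2, Hypothesis 2 (Analytic Plan), the outcomes are total home/car bans and child SHSe. The section opens its modelling with: "The main analysis will use GLMM, first to assess the intervention effect alone and then including covariates". The covariates are not listed; NRT use is the only one mentioned. It continues: "First, we will investigate immediate intervention effects based on change from baseline to 6-weeks post-intervention". Change from 6 weeks to 6 months follows as a maintenance analysis, and overall change uses GEE, "examining linear and quadratic terms for time, group, and group \times time interactions as explanatory variables".

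Ban status is available at baseline. Item 7 of the Baseline Assessment derives it from the child SHSe questions (caregivers reporting no smoking in the listed places "will be considered to have a complete smoking ban"), and Table 1 schedules those questions at T0, T1 and T2. Child saliva for cotinine is also taken at baseline.

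Preliminary Analyses adds baseline variables as covariates only when the arms are found to differ on them.

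The Power subsection says the trial can "detect a difference of 12% with 80% power with 300 per group assuming a rate of between 50% and 65% in the HHC group", and adds: "Using multiple imputation and 375 per group, we could detect a difference of 11% with 80% power". It names no model, time point, alpha or baseline correlation for this figure. The 300 comes from "potential attrition of approximately 20% at 6 months" applied to 750 caregivers.

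**The concern.** Randomisation makes any baseline difference in ban rate a matter of chance. A change contrast, or a group-by-time term with free baseline means, subtracts that chance difference in full. Conditioning on baseline subtracts only the part that predicts follow-up. So a primary aim may give up precision that the trial already holds the data to recover.

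The GEE does not escape this. A quadratic time term needs three time points and the trial has only three assessments, so baseline must be one of the responses, and no equal-baseline constraint is stated. Adding covariates in a second step does not settle it either, because the baseline value is not named there and the general rule makes its entry depend on the data.

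**Working it through.** **Inputs.** From the Power subsection: d = 0.12, n = 300 per arm, HHC rate 50% to 65%. Assumed, because the plan is silent: two-sided alpha 0.05, baseline ban rate b (10% to 65%) and baseline-to-follow-up correlation ρ. Write v(p) = p(1−p), with pc and pt the HHC and SBIRT follow-up rates.

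**1. The plan's own figure.** For two proportions at follow-up with p̄ their mean, power = Φ{[d − 1.96√(2v(p̄)/n)] / √[(v(pc)+v(pt))/n]}. For 50% versus 62%: 1.96 × 0.04053 = 0.0794, and (0.12 − 0.0794)/0.04023 = 1.01, giving 84.3%. For 65% versus 77% it is 90.2%. With 375 per group and 11 points it is 85.9% to 91.2%. The difference detectable at 80% is 10.4 to 11.3 points (300) and 9.4 to 10.2 points (375). The stated 12 and 11 points are therefore conservative for a follow-up-only comparison.

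**2. Variance per arm (times n), with p that arm's follow-up rate.**
- Follow-up only: v(p)
- Change: v(p) + v(b) − 2ρ√[v(p)v(b)]
- Conditioned on baseline: (1−ρ²)v(p)

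Change minus conditioned is (√v(b) − ρ√v(p))², which is never negative. The ordering needs no knowledge of ρ or b; only the size does.

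**3. Power = Φ(d/SE − 1.96).** Worked case: HHC 50%, b = 50%, ρ = 0.3.
- Change: 0.350 + 0.340 = 0.690; SE = √(0.690/300) = 0.0480; 0.12/0.0480 − 1.96 = 0.54; power 71%.
- Conditioned: 0.91 × 0.4856 = 0.442; SE = 0.0384; 0.12/0.0384 − 1.96 = 1.17; power 88%.

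Follow-up only on the same basis is 85%.

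| HHC 50%, 12 points, 300 per arm | Change | Conditioned |
|---|---|---|
| b 50%, ρ 0.2 | 65% | 86% |
| b 50%, ρ 0.3 | 71% | 88% |
| b 50%, ρ 0.5 | 84% | 93% |
| b 50%, ρ 0.7 | 97% | 99% |
| b 20%, ρ 0.3 | 79% | 88% |
| b 20%, ρ 0.5 | 90% | 93% |
| b 10%, ρ 0.3 | 84.5% | 87.8% |

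At HHC 65% with b = 65%, change versus conditioned is 76% versus 93% (ρ 0.3) and 89% versus 97% (ρ 0.5). A group-by-time contrast on the logit scale behaves similarly to change: about 70% at ρ 0.3 and 84% at ρ 0.5 for HHC 50%, b 50%.

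**4. When would change miss the stated 80%?** Set SE = 0.12/2.80 = 0.0428 and solve for ρ. With b equal to the HHC rate, the limit is ρ = 0.44 (HHC 50%) or 0.36 (HHC 65%). With b = 20% it is 0.32 or 0.24; with b = 10%, about 0.19 or 0.06. Change falls below a follow-up-only test at a different point, ρ of about 0.5 when b equals the HHC rate.

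**5. Limit on the low-baseline rows.** Two binary variables with rates b < p cannot correlate above √{b(1−p)/[(1−b)p]}. For b = 20% that is 0.50 at p = 50% and 0.39 at p = 62%; for b = 10% it is 0.33 and 0.26. The rows b 20%, ρ 0.5 and b 10%, ρ 0.3 are therefore slightly beyond what the SBIRT arm could show and are approximate.

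**The case against.** Four points deserve weight.

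- **The power figure may not belong to the change step.** The 300 per group rests on 6-month attrition, whereas the change sentence concerns 6 weeks, for which no retention is projected. The section names a GLMM as its main analysis and also speaks of two measurement points, so the 12 points may refer to a follow-up comparison. This stands.
- **Both unknowns drive the size.** All caregivers are daily smokers and the ban definition is strict, so baseline bans could be far rarer than the 50% to 65% assumed for HHC at follow-up. The gain then shrinks. This stands.
- **Baseline adjustment is a possible reading.** The plan does not define change for a binary ban. Its general approach uses repeated-measures analysis of covariance controlling for baseline differences for secondary outcomes, and Follow-up Assessments lists bans and SHSe among these. For 6-month child cotinine, the Aim 1 text plans a t-test and then analysis of covariance. So conditioning is left open, not excluded. But the outcomes named under that general approach are all caregiver outcomes, and covariate entry still depends on a baseline difference being found.
- **Only efficiency is at stake.** Under randomisation the change contrast is unbiased, with correct type I error. This stands.

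A reader might infer that the stated 80% is overstated unless the correlation exceeds about 0.5. The documents do not support that. The 0.5 crossover is against a follow-up-only test, whose own power is 84% to 90%. At ρ 0.5 the change analysis gives 84% (HHC 50%) or 89% (HHC 65%) with b equal to the HHC rate, both above the stated 80%.

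**Conclusion.** The point holds as an efficiency gap, not as an error in the stated power. Aim 2 describes its immediate effect as change from baseline and its overall effect through group-by-time terms with free baseline means, and leaves conditioning on baseline to a data-dependent rule. Conditioning is at least as efficient for every correlation and baseline rate.

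The gain at HHC 50% is about 17 power points at ρ 0.3 and 9 at ρ 0.5 if half of caregivers report a ban at baseline. It is about 9 and 3 points if a fifth do, and about 3 points at ρ 0.3 if a tenth do. The 17-point figure is one scenario and should not be quoted alone. All figures assume two-sided 0.05 and that change means a simple difference or an unconstrained group-by-time contrast.

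Whether the change analysis falls short of the stated 80% cannot be settled, because the correlation, the baseline ban rate, and the analysis and time point being powered are all unstated.

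**What to change.** - In the Aim 2 section, replace the change-based step with a between-arm comparison of ban rates at 6 weeks and at 6 months, with baseline ban status as a pre-specified covariate in the first model, whether or not the arms differ at baseline.
- In the longitudinal GEE, either use the two follow-ups as responses with baseline as a covariate, or keep baseline as a response and constrain the arm means to be equal there.
- Treat caregiver-reported SHSe and log child cotinine the same way, each with its own baseline value.
- In the Power subsection, state which analysis and time point the 12-point figure refers to, and the alpha. If a change analysis is kept, give the correlation and baseline rate it assumes.

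The cost is a few sentences of analysis-plan wording, with no new data, visits or participants. Missing baseline items can be handled by the multiple imputation already planned. Under conditioning, the 12-point figure is conservative whatever the correlation.
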